One goal of the proposed clinical investigation is to test the null hypothesis that the population mean is 82.16 points. The criterion for significance (alpha) has been set at 0.05. The test is 2-tailed, which means						

that effects in both directions will be interpreted. With the proposed sample size of 10 cases, the clinical investigation will have power of 80.3% to yield a statistically significant result. This computation assumes that the population from which the sample will be drawn has a mean of 82.16 points with a standard deviation of 16.76 points. The observed value will be tested against a theoretical value (constant, non-inferiority margin) of 65.40 points.

IBM SPSS Sample Power Output – Screenshot

Estimated overall drop-out rate is 56% which leads to the requirement of enrolling additional 6 subjects into the clinical investigation.

Sample Size	Number of subjects to be enrolled: 16 subjects (rounded up to 20 subjects)
Overall Sample Size (multiplied by number of indications (=5))	100 subjects

Table 2: Sample Size Justification

In conclusion, the calculated number of subjects to be enrolled (10) plus the estimated overall drop-out rate of 56% predicts enrollment of 20 subjects per cleared indication (five) to reflect the underlying subject population adequately. As a result, an enrollment target of 100 subjects in total will be aspired.

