11.3. ANALYSIS AND EVALUATION

11.3.1. Statistical Analysis

Evaluation elements are defined as the questions on the CRF/eCRF. The SAP lists all evaluation elements and secondary elements which will be based on calculations between two or more evaluation elements.

All quantitative variables, including those based on calculations (secondary elements), will be analyzed with a case summary evaluation before the detailed characteristics and parameters can be evaluated. A case summary contains a listing of the number of valid cases/values, missing cases/values (if any) and total cases/values in the specific analysis. In general, as central position parameter for quantitative variables the mean, median and mode will be analyzed. As variation parameter the standard deviation, 95% confidence interval of the mean, interquartile range and range (based on maximum and minimum) will be calculated. All quantitative variables will be assessed for normality using the Shapiro-Wilk test. For optional visualization of quantitative variables, box-and-whisker plots will be used. Additional analyses like skewness and kurtosis measures or standard errors are optional also.

All qualitative variables, including those based on summaries (secondary elements), will be analyzed listing the proportions, frequencies, column and row totals, and missing proportion, if any.

The SAP reflects this approach and specifies the variables characteristics (quantitative or qualitative) in detail together with the related analysis strategy. This also includes calculation and summaries based on primary elements and the required analysis.

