11.3.2. Primary Analysis / Endpoint

The objective of the clinical investigation is to demonstrate non-inferiority (equal or better) of the ASES Shoulder Score in relationship to the officially cleared indications in comparison to respective clinical outcome data in the scientific literature.

[figure not shown]
Data collection of ASES Shoulder Score will start pre-operatively and will be collected according to schedule in Table 1. This will be repeated annually in all subjects who have the total or partial prosthesis with full or partial implant survival (including all subjects without removal of all endo-prosthesis components).

The 24 months post-operative results for subjects implanted with ReUnion TSA System will be compared to a historical group and results reported by respective clinical outcome data in the scientific literature. The benchmark sources and values will serve as the control group for the ReUnion TSA System subjects.

Higher ASES Shoulder Score results are linked to better subject results and vice versa.

The clinical investigation endpoint is non-inferiority to the control, meaning the clinical investigation result should be equal or better than the control. In this clinical investigation, an equal or better ASES Shoulder Score result means equal or more (\geq). As only results from samples will be captured, results are mostly estimates of the true population parameter. These estimates vary by a certain area, where it is expected that the true population parameter falls within. Based on this, it is required to specify a lower limit for the acceptable difference or zone of indifference, denoted as $-\theta$.

Hypotheses are developed to allow for a comparison of the 24 months post-operative ASES Shoulder Score effectiveness / performance between the two underlying populations. The 24 months post-operative ASES Shoulder Score is the primary endpoint of this clinical investigation. Hypothesis tests will be one-sided with a significance level α of 5%.

Hypothesis	Equations	Interpretation
Null (H_0)	$A - B < -\theta$	Central tendency of A is inferior to the central tendency of B.
	ReUnion TSA System – Control (Benchmark) $< -\theta$	
Alternative (H_1)	$A - B \geq -\theta$	Central tendency of A is non-inferior to the central tendency of B.
	ReUnion TSA System – Control (Benchmark) $\geq -\theta$	
		
Possible Evidence (p)	Possible Decisions	Possible Conclusions – ASES score

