p-value $> \alpha$ (0.05)	Fail to reject null hypothesis (H_0)	ReUnion TSA System $<$ Control (Benchmark) Insufficient evidence to reject the null hypothesis ($H_0: A - B < -\theta$) at the pre-determined significance level of 5%.
p-value $\leq \alpha$ (0.05)	Reject null hypothesis (H_1)	ReUnion TSA System \geq Control (Benchmark) Sufficient evidence to reject the null hypothesis ($H_0: A - B < -\theta$) at the pre-determined significance level of 5%.

To test non-inferiority, the 24 months mean ASES Shoulder Score result of the ReUnion TSA System group will be compared to the mean estimate of the control group, 82.16 points.

To be able to identify an acceptable difference or zone of indifference ($-\theta$), the pooled standard deviation of the ASES Shoulder Score result at 24 months post-operative in the control group (Benchmark) was used as lower limit (pooled standard deviation of control is 16.76 points). The lower maximum acceptable difference ($-\theta$) is 51.87 points (mean of control - θ or 82.16 - 16.76 = 65.40 points).

Based on the underlying distribution of the data and the result of the normality assessment, either the parametric one-sample t-test or the non-parametric one-sample sign test will be used to compare the 24 months post-operative ASES Shoulder Score results of the ReUnion TSA System against the value of 65.40 points.

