p-value > α (0.05)	Fail to reject null hypothesis (H0)	ReUnion TSA System < Control (Benchmark) Insufficient evidence to reject the null hypothesis (H0: A - B < - θ) at the pre-determined significance level of 5%.
p-value \leq α (0.05)	Reject null hypothesis (H1)	ReUnion TSA System \geq Control (Benchmark) Sufficient evidence to reject the null hypothesis (H0: A - B < - θ) at the pre-determined significance level of 5%.

Table 3.1.1: Research Goal and Hypothesis (Primary Endpoint)

To test non-inferiority, the 24 months mean ASES Shoulder Score result of the ReUnion TSA System group will be compared to the mean estimate of the control group, 82.16 points.

To be able to identify an acceptable difference or zone of indifference ($-\theta$), the pooled standard deviation of the ASES Shoulder Score result at 24 months postoperative in the control group (Benchmark) was used as lower limit (pooled standard deviation of control is 16.76 points). The lower maximum acceptable difference ($-\theta$) is 65.40 points (mean of control - θ or 82.16 – 16.76 = 65.40 points).

Based on the underlying distribution of the data and the result of the normality assessment, either the parametric one-sample t-test or the non-parametric one-sample sign test will be used to compare the 24 months postoperative ASES Shoulder Score results of the ReUnion TSA System against the value of 65.40 points.

The analysis of the primary endpoint / objective will be conducted when all subjects have completed the 24 months postoperative including the ASES Shoulder Score.

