4.10. ASSUMPTIONS

In case of deviation from assumptions (e.g. normality), non-parametric methods will be used for analysis. No transformation of such data will be performed.

5. Population and Progress

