6.6. ANALYSIS OF CI ENDPOINTS

Evaluation Variable / Question	Level of Measurement	Analysis Plan					
Endpoints – Primary Endpoint							

Use variable Total ASES Shoulder Score 24 Months [points]: Based on the underlying distribution of the data and the result of the normality assessment, either the parametric one-sample t-test or the non-parametric one-sample sign test will be used to compare the 24 months postoperative ASES Shoulder Score results of the ReUnion TSA group against the lower maximum acceptable difference ($-\theta$) of 65.40 points.
 
The analysis of the primary endpoint will be part of the final report.
							

Table 6.6.1: Endpoints – Primary Endpoint Tables List

Evaluation Variable / Question	Level of Measurement	Recode and Analysis Plan	Inclusion		
Adverse Events – Time to (earliest) Device-Related Adverse Event / Incident			IR	FR	N/A
Creation of variable Difference between Date of Surgery [dd.mm.yyyy] and Date of First Device Related Adverse Event [dd.mm.yyyy] in days / (Variable(s): VISITDT; AEONSTDT)	Quantitative, ratio	Case summary with number and percentage of valid cases/values, missing cases/values (if any) and total cases/values. Mean, median, interquartile range, maximum, minimum, standard deviation, 95% confidence interval for mean, Shapiro-Wilk Test.		X	
Creation of variable Difference between Date of Surgery [dd.mm.yyyy] and Date of “most recent” Visit [dd.mm.yyyy] in days / (Variable(s): VISITDT)	Quantitative, ratio	N/A (Analyzed above), used for survivorship		X	

Create new variable “Grouping variable – First Device Related Adverse Event” (Variable(s): AEONSTDT)	Qualitative, nominal	- censored = survivors - events = first (earliest) Device Related Adverse Event		X	
Create new variable “Combined Time – First Device Related Adverse Event” (Variable(s): AEONSTDT)	Quantitative, ratio	- Use time between surgery and “most recent” visit for surviving subjects - Use time between surgery and first device related adverse event for subjects with device related adverse event		X	

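### The normality check can switch the primary test from the mean to the median against the same mean-based limit of 65.40; with left-skewed scores the one-sided 5% error rate is exceeded

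*Protocol*

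**What the plan says.** Protocol 11.3.2 and SAP 3.1.1 frame the comparison in means: "To test non-inferiority, the 24 months mean ASES Shoulder Score result of the ReUnion TSA System group will be compared to the mean estimate" for the controls, which is 82.16. The limit is the control mean minus the control SD, 82.16 − 16.76 = 65.40. Protocol 11.1 uses the same value in the sample size calculation: "The observed value will be tested against a theoretical value (constant, non-inferiority margin) of 65.40 points".

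The test itself is left to the data. Protocol 11.3.2 makes it depend on the distribution and on how normality is judged, and says that "either the parametric one-sample t-test or the non-parametric one-sample sign test will be used to compare the 24 months post-operative ASES Shoulder Score results" against 65.40. SAP 6.6 repeats that "either the parametric one-sample t-test or the non-parametric one-sample sign test will be used". The normality assessment is given in Protocol 11.3.1: "All quantitative variables will be assessed for normality using the Shapiro-Wilk test". SAP 4.10 makes the switch binding: "In case of deviation from assumptions (e.g. normality), non-parametric methods will be used for analysis". It also rules out transformation.

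The hypothesis tables in Protocol 11.3.2 and SAP 3.1.1 name neither mean nor median. The null reads "Central tendency of A is inferior to the central tendency of B" and the alternative "Central tendency of A is non-inferior to the central tendency of B". The test is one-sided at 5%.

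**The concern.** A one-sample sign test against 65.40 counts the subjects above 65.40 and asks whether they are more than half. That is a statement about the median. The limit was built from benchmark means, and no median benchmark or median limit appears in either document. So the data decide which parameter the primary claim is about, while the number it is tested against stays on the mean scale. This part needs no assumption about the scores.

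What follows depends on skewness. If scores are left-skewed, the median exceeds the mean. A device whose true mean sits at the limit, or slightly below it, can then have well over half of its subjects above 65.40 and pass the sign test. The report would show the low mean alongside, but the formal conclusion would be non-inferiority.

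**Working it through.** **1. The plan's own figure.** For a one-sample t-test with n = 10, the noncentrality is (82.16 − 65.40)/16.76 × √10 = 3.162 on 9 df. Two-sided α = 0.05 gives power 80.31%, which matches the stated 80.3%. The sample size therefore rests on a test of the mean; the sign-test branch is not covered by it.

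**2. Inputs.** Limit 65.40; planning SD 16.76; benchmark SDs from 10.1 to 22.4 (Protocol Table 2); one-sided 5%. Evaluable n is taken as 100 (no loss) and 100 × (1 − 0.56) = 44 (the plan's drop-out rate). Three assumptions are not stated for this purpose in the documents: a 0–100 score range, a beta shape, and Shapiro-Wilk judged at 0.05 (the general threshold in Protocol section 11 and SAP 4.7).

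**3. Sign test critical counts.** The smallest r with P(Bin(n, ½) ≥ r) ≤ 0.05 is 28 of 44 (exact size 4.8%) and 59 of 100 (4.4%). As a test of the median it keeps its level.

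**4. The same test when the mean is at the limit.** Take a beta on 0–100 with mean 65.40 and SD 16.76. With M = 0.654 and V = 0.1676² = 0.02809, M(1 − M)/V − 1 = 7.056, so a = 0.654 × 7.056 = 4.61 and b = 0.346 × 7.056 = 2.44. This has skewness −0.41, median 66.9 and P(score > 65.40) = 0.533. The sign test alone then rejects with probability P(Bin(44, 0.533) ≥ 28) = 11.0% and P(Bin(100, 0.533) ≥ 59) = 14.8%.

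**5. The full two-step rule.** Shapiro-Wilk p ≤ 0.05 leads to the sign test, otherwise to the t-test. True mean 65.40, 20,000 simulated trials per cell, shown as n = 44 / n = 100:

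| SD | Skewness | Sent to sign test | Two-step rule rejects | t-test alone rejects |
|---|---|---|---|---|
| 10.1 | −0.26 | 8% / 15% | 6.8% / 8.1% | 5.5% / 5.7% |
| 13.1 | −0.33 | 11% / 26% | 7.8% / 9.9% | 5.6% / 5.5% |
| 16.76 | −0.41 | 20% / 56% | 9.0% / 13.9% | 5.5% / 5.6% |
| 22.4 | −0.50 | 58% / 98% | 14.0% / 23.0% | 5.9% / 5.5% |

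The excess grows with n: more data make Shapiro-Wilk reject more often and sharpen the test of the wrong parameter.

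**6. Controls and stronger skew** (10,000 trials each). Normal scores: 5.4% / 5.1%. Right skew of +0.5: 3.8% / 2.7%, so the direction depends on the skew. Left skew of −1.0 at SD 16.76, generated as 65.40 + kh − Gamma(k, scale h) with k = 4/1² = 4 and h = 16.76/√4 = 8.38: median 68.2, two-step 21% / 36%, t-test 6.9% / 6.1%.

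**7. Just below the limit.** At a true mean of 64 the two-step rule passes 3.5% / 3.9% (SD 16.76) and 7.6% / 10.5% (SD 22.4). The t-test passes 0.8% to 2.4%.

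**8. At the planned mean.** A beta with mean 82.16 and SD 16.76 has skewness −1.23. Shapiro-Wilk rejects in 99.7% of trials at n = 44 and in essentially all at n = 100, so under this shape the sign test is the primary analysis in practice. The two-step rule passes 99.97% / 100% and the t-test 99.99% / 100%.

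**The case against.** The strongest reply is that the hypotheses speak of central tendency, which can mean the median, and that the sign test keeps its level for the median (step 3). On that reading there is an unfixed target, not an inflated error rate. But the text beside the tables names the mean, 65.40 is derived from means, and a loose term does not help when the data still choose the parameter. The reply does show that the excess is an excess relative to the mean.

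Second, the documents give no skewness, score range or patient-level data. That stands: the error figures are conditional, and normal or right-skewed scores show no material excess.

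Third, some inputs are soft. The SD of 22.4 comes from a source that Table 2 flags as possibly a confidence interval; the largest unflagged SD, 21, gives 13.1% / 20.3%. A skewness of −1.5 gives 37% / 62%, but that generated shape has a ceiling of 65.40 + 22.35 = 87.75, below three of the benchmark means (88.4, 90.3 and 94.4), so I do not rely on it.

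Fourth, the plan also reports the mean with its 95% confidence interval. In null simulations (beta, SD 10.1 to 22.4) about 79% to 88% of sign-test passes came with an interval reaching below 65.40. A careful reader would usually see the conflict, but the formal conclusion would still stand.

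Last, the practical reach is narrow, because the planned mean lies 16.76 points above the limit. That also stands.

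**Conclusion.** The concern holds. The primary test can move from the mean to the median on the strength of the data, against a limit justified only for the mean. Given left skew, the stated one-sided 5% is not kept: about 7% to 14% at 44 evaluable subjects and 8% to 23% at 100 for beta-shaped scores across the benchmark SDs, with 9% and 14% at the planning SD. A skewness of −1.0 takes this to 21% and 36%. These figures assume a 0–100 range, the shapes described and a mechanical 0.05 reading of Shapiro-Wilk. A small part of the excess is the t-test's own error under skew. The result is unlikely to change if the device performs as planned; what is at risk is error control near the limit, and clarity about what has been shown. It should be corrected before the 24-month data are analysed.

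**What to change.** In Protocol 11.3.2, SAP 3.1.1 and SAP 6.6, replace the sentence offering two tests with:

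> The primary test is the one-sample t-test of the mean 24-month ASES Shoulder Score against 65.40, one-sided at 5%, whatever the Shapiro-Wilk result. The sensitivity analysis is a bootstrap one-sided 95% lower confidence bound for the mean (the lower limit of a two-sided 90% interval). The median is reported descriptively.

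Delete the sign-test branch. In both hypothesis tables, write mean in place of central tendency. Add to SAP 4.10 that the rule on non-parametric methods does not apply to the primary endpoint.

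The bootstrap bound must be the one-sided 95% bound. In 2,000 null trials with 1,000 resamples each, it rejected 6.0% / 6.0% (SD 16.76) and 6.7% / 5.9% (SD 22.4) at n = 44 / 100. The lower limit of a two-sided 95% interval rejected 2.9% to 3.8% and would not match the test.

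The cost is a few sentences and no extra subjects. Under the plan's assumptions power stays above 99.9% at 44 evaluable. The one drawback is that under strong left skew the t-test runs somewhat above 5%: 6.9% at skewness −1.0 and 8.0% at −1.5 with n = 44, the highest in the settings behind this proposal. The change removes most of the excess, not all of it.

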11.3.3. Secondary Endpoints

The incidence of device-related AEs and implant survivorship will be assessed up to 10 years after the index procedure and monitored through collection and analyses. These analyses will be part of the annual and final reports.

Furthermore, time to (earliest) device-related AEs will be analyzed as well. For analysis of the time to the (earliest) device-related AEs as well as the time to secondary procedure (revision, removal, reoperation), the Kaplan-Meier method will be used. The time between surgery and the last available assessment will be used together with the time between date of surgery and the date of secondary procedure. Considered variables, the level of measurement and the planned analysis steps are listed in detail in the SAP.

11.3.4. Additional Analyses

Additional analyses are outlined in the subsequent sections. Analysis details (variables, level of measurement, planned steps) are listed in-depth in the SAP.

- **Mortality**

For analysis of the time to death or mortality, the Kaplan-Meier method will be used. The times between surgery and the last available assessment will be used together with the times between date of surgery and the date of death. This analysis will be part of the annual and final reports.

- **ASES Total Score – Within subject changes by visit**

The within subject score changes of the ASES Shoulder Score from visit to visit will be analyzed to help identify the changes on the subject level. This analysis will be part of the annual and final reports.

11.4. MISSING DATA / SAP DEVIATIONS

The intent is to collect as complete dataset as possible. Nevertheless, in some situations missing data cannot be avoided. The reports and tables therefore will show the number and percentage of missing cases for each analyzed variable in relation to the enrolled cases for each post-operative assessment

Any deviations from the SAP will be listed in the annual or final reports.

11.5. REPORTS

11.5.1. Interim Analysis and Reports

Interim analyses will be performed on a yearly basis. The progress of the clinical investigation will be reported together with the interim results on the variable level according to the analysis plan.

The analysis of the primary endpoint will be part of the related interim / annual report when all subjects have completed the 24 months post-operative including the ASES Shoulder Score.

11.5.2. Final Analysis and Reports

The full final report with complete analysis including progress and conduct reporting will be created at the end of this clinical investigation.

12. Clinical Investigation Plan Deviations

A CIP deviation is a departure from the approved CIP that is not implemented or intended as a systemic change. All CIP deviations are recorded and reported to each site's IRB in accordance with the respective site's IRB policies.

13. Adverse Events

As this CIP is being carried out to satisfy the post-market requirements to support safety and efficacy/performance according to the European Medical Device Regulation (EU MDR), categorization and definition of device-related adverse events will follow the guidelines outlined in the EU MDR as “incident” reporting.

13.1. DEFINITIONS

- **An Adverse Device Effect (ADE)** is defined as any untoward or unintended response to the clinical investigation treatment; and/or a medical response which may have a causal relationship to the treatment.
- **An Incident** is defined as any malfunction or deterioration in the characteristics or performance of a device made available on the market, including use-error due to ergonomic features, as well as any inadequacy in the information supplied by the manufacturer and any undesirable side-effect.
- **A Serious Adverse Device Effect (SADE)** is defined as any ADE that results in consequences characteristic of a SAE or might lead to the consequences if suitable action or intervention is not taken; causes considerable interference with the subject's usual activities and may be incapacitating or life-threatening, including those events resulting in a subject's disability or permanent damage, or required intervention to prevent disability or permanent damage; results in a life-threatening illness or injury; and/or results in death (fatal).
- **A Serious Incident** is defined as any incident that directly or indirectly led, might have led or might lead to any of the following:
 - the death of a patient, user or other person;
 - the temporary or permanent serious deterioration of a patient's, user's or other person's state of health;
 - a serious public health threat
- **An Unanticipated Adverse Device Effect (UADE)** is defined as an AE not described in the informed consent, CIP or device labeling which has resulted in any of the consequences of a SAE or which might have led to any of the consequences of a SAE if suitable action had not been taken, intervention had not occurred, or if circumstances had been less opportune.

